#### **10.4 Subgroup analyses**

Predefined subgroup analyses will be performed to test for interaction between a specific variable and the treatment.

The following subgroups will be investigated:

- Intermediate grade stenosis (50-70%), high grade stenosis (>70%) versus occlusion of the ICA
- Occlusion location (ICA, M1, M2)
- Collateral score on baseline CTA (0,1,2 and 3)
- Performance of PTA during EVT (yes or no)
- NIHSS stroke scale severity (NIHSS >15 points versus NIHSS ≤15 points)
- Age (>80 years versus ≤ 80 years)
- Onset to groin puncture time (tertiles)
- ASPECT score (>6 versus ≤ 6)
- prior IVT (yes/no)

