## 5. TREATMENT OF SUBJECTS

### 5.1 Investigational product/treatment

In patients allocated to the intervention group, the carotid artery stenosis will be stented during the EVT. The CAS may be done just before the intracranial thrombus removal or directly after (at the discretion of the interventionist). In case of unsuccessful intracranial reperfusion (TICI score < 2b), it is still recommended to perform CAS. In addition, if the first DSA run demonstrates intracranial recanalization but confirms a high-grade carotid artery stenosis, it is still recommended to perform CAS. Crossover to deferred treatment is strongly discouraged and will be considered a protocol violation unless a valid reason has been reported by the local PIs.

The patients allocated to the control group are being treated with EVT, without stenting of the carotid artery stenosis. Percutaneous transluminal angioplasty (PTA) of the carotid artery stenosis is allowed to gain access in order to remove the intracranial occlusion. Crossover to stenting during EVT is strongly discouraged. Crossovers without a valid reason according to the executive committee will be considered a protocol violation. If the patient recovers to a non-disabling stroke after EVT, CEA or CAS is offered according to the guidelines (usually CEA or CAS within 2 weeks after stroke onset). In case of a persistent disabling stroke, patients receive best medical treatment, without intervention of carotid artery stenosis.

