## 7. NON-INVESTIGATIONAL PRODUCT

### 7.1 Name and description of non-investigational product(s)

EVT will be performed with either stent retriever or thrombus aspiration catheters at the discretion of the interventionist. Devices approved for this study are listed in the table below. If necessary the use PTA of the carotid artery stenosis is allowed in the control group.

Device name	Manufacturer	Description
Embotrap	Cerenovus	Stent retriever
Eric	Microvention	Stent retriever
Solitaire	Medtronic	Stent retriever
Catch	Balt	Stent retriever
Preset	Phenox	Stent retriever
Trevo	Stryker	Stent retriever
Tigertriever	RapidMedical	Stent retriever
Nimbus	Cerenovus	Stent retriever
NeVa	Vesalio	Stent retriever
ACE64/68/Red	Penumbra	Aspiration catheter
4Max	Penumbra	Aspiration catheter
3Max	Penumbra	Aspiration catheter
Sofia 5F or Sofia Plus	Microvention	Aspiration catheter
Embovac	Cerenovus	Aspiration catheter
Catalyst	Stryker	Aspiration catheter
AXS Vecta	Stryker	Aspiration catheter
React	Medtronic	Aspiration catheter
Merci	Stryker	Balloon guiding catheter
Flowgate2	Stryker	Balloon guiding catheter
Cello	Medtronic	Balloon guiding catheter

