#### **8.2 Randomization, blinding and treatment allocation**

The randomization will be performed by a computer and web-based procedure, using permuted blocks. Back-up by telephone will be provided. Randomization is allowed when the CTA at baseline demonstrates an ipsilateral high-grade stenosis (>50%) or occlusion of the proximal ICA of presumed atherosclerotic origin. Although DSA is more reliable to distinguish carotid pseudo-occlusions from cervical atherosclerotic lesions in the ICA, randomization during the EVT can be very challenging and might lead to lower inclusion rates. And CTA has been shown to have acceptable diagnostic accuracy for true cervical ICA lesions. Only in case of significant doubt by the interventionist if there is a true cervical atherosclerotic lesion in the carotid artery, randomization is also allowed after the first angiographic run of the carotid artery that confirms the cervical atherosclerotic lesion. Randomization will be stratified for center. Both the patient and treating physicians are aware of the treatment assignment. The 90 days follow up will be performed by certified research personnel blinded for the treatment allocation. The assessment of secondary endpoints will not be blinded as for several secondary endpoints it will be obvious whether the patient was treated with CAS or not. Information on treatment allocation will be kept separate from the main study database. An independent trial statistician will combine the data on treatment allocation with the clinical data in order to report to the data safety monitoring board (DSMB). The trial steering committee will be kept unaware of the exact results of the interim analyses on efficacy and safety. Only the recommendation to continue, modify or stop the trial will be communicated.

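### Section 10.4 predefines a treatment interaction test on PTA during EVT, which is decided after randomisation under a condition written for the control arm only, so the test can show an interaction that does not exist

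*Protocol*

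**What the plan says.** Section 10.4 introduces its list with "Predefined subgroup analyses will be performed to test for interaction between a specific variable and the treatment". One of the nine variables is "Performance of PTA during EVT (yes or no".

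Four other statements bear on this item:

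- **Timing.** Section 8.2 states: "Randomization is allowed when the CTA at baseline demonstrates an ipsilateral high-grade stenosis (>50%) or occlusion of the proximal ICA". The exception, for a doubtful lesion, is that "randomization is also allowed after the first angiographic run of the carotid artery that confirms the cervical atherosclerotic lesion". In both cases allocation comes before the decision on PTA.
- **Blinding.** Section 8.2 also states: "Both the patient and treating physicians are aware of the treatment assignment".
- **Control arm.** Section 5.1 states: "Percutaneous transluminal angioplasty (PTA) of the carotid artery stenosis is allowed to gain access in order to remove the intracranial occlusion". Section 7.1 adds: "If necessary the use PTA of the carotid artery stenosis is allowed in the control group".
- **Stenting arm.** Section 5.1 says the lesion is stented during EVT and gives no indication for PTA and no limit on it. Section 5.2 mentions PTA alongside stenting only in connection with bradycardia.

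The protocol does not describe the PTA subgroup as exploratory or non-randomised, and does not confine it to one arm.

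**The concern.** A subgroup interaction test compares the treatment effect between strata. Randomisation protects that comparison only if stratum membership cannot depend on the arm. PTA during EVT does not meet this condition. It happens after allocation, the operator knows the arm, and the access condition is written for controls alone.

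Controls who receive PTA are thus likely to be those whose carotid lesion was hard to pass. Patients in the stenting arm who receive PTA need not be selected in this way. If hard-to-pass lesions go with worse outcome, the PTA-yes stratum sets selected controls against less selected stented patients, and stenting looks better there than it is. In the PTA-no stratum the controls have lost their difficult cases, and stenting looks worse than it is. The two distortions run in opposite directions, so together they look like an interaction. A larger sample would not remove the bias.

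At stake is the reading of one predefined subgroup result.

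**Working it through.** The protocol states no figure for this item, so there is none to reproduce. The check asks how large a false interaction could be when treatment has no effect in any patient.

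**Inputs from the protocol (section 4.5).** 300 patients per arm; deferred-group mRS distribution 6.9 / 20.2 / 17.9 / 16.4 / 17.2 / 8.0 / 13.4% for mRS 0 to 6; two-sided alpha 0.05, which the protocol states for the sample size and which is assumed here for the interaction test.

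**Assumed inputs (the protocol gives none).** Difficult access in a share π = 0.30 of patients; a cOR for better outcome with difficult access (access cOR) of 0.70, 0.50 or 0.35; PTA probabilities q0 without and q1 with difficult access, set separately by arm.

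**Step 1: share of difficult-access patients in each stratum of an arm.**

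- PTA yes: s = π·q1 / [π·q1 + (1−π)·q0]
- PTA no: s = π(1−q1) / [π(1−q1) + (1−π)(1−q0)]

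For controls with q0 = 0.10 and q1 = 0.80:

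- PTA yes: 0.24 / (0.24 + 0.07) = 0.774
- PTA no: 0.06 / (0.06 + 0.63) = 0.087

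For the stenting arm with PTA at 70% regardless of access, the share is 0.30 in both strata.

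**Step 2: approximate apparent treatment effect in a stratum.** ln(apparent cOR) ≈ ln(access cOR) × (s in stenting arm − s in controls).

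Access cOR 0.50, ln = −0.693:

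- PTA yes: −0.693 × (0.30 − 0.774) = 0.329, cOR 1.39
- PTA no: −0.693 × (0.30 − 0.087) = −0.148, cOR 0.86
- interaction ratio: exp(0.329 + 0.148) = 1.61

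Access cOR 0.70, ln = −0.357:

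- PTA yes: 0.169, cOR 1.18
- PTA no: −0.076, cOR 0.93
- interaction ratio: exp(0.245) = 1.28

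If PTA marks difficult access perfectly in controls (s = 1 and 0) and is unrelated to access in the stenting arm, the ratio is 1 / access cOR: 1/0.70 = 1.43 (strata 1.28 and 0.90) and 1/0.50 = 2.0 (strata 1.62 and 0.81).

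**Step 3: simulation for rejection rates.** Proportional-odds models with and without the treatment-by-PTA term were compared by likelihood-ratio test at 0.05, with 300 to 400 runs per row (Monte Carlo error about 1 to 3 points). PTA rates are given as without / with difficult access.

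| Control PTA | Stenting-arm PTA | Access cOR | Spurious ratio | Rejection |
|---|---|---|---|---|
| 10% / 60% | 50% / 60% | 0.70 | 1.18 | 8.5% |
| 10% / 60% | 90% / 90% | 0.70 | 1.21 | 8% |
| 10% / 80% | 70% / 70% | 0.70 | 1.29 | 13% |
| 0% / 100% | 50% / 50% | 0.70 | 1.42 | about 20% |
| 10% / 60% | 50% / 60% | 0.50 | 1.38 | 17% |
| 10% / 80% | 70% / 70% | 0.50 | 1.63 | 31% |
| 10% / 80% | 70% / 70% | 0.35 | 2.06 | 62% |
| 10% / 80% | 10% / 80% | 0.50 | 0.99 | 4.7% |
| 10% / 80% | 70% / 70% | 1.0 | 1.01 | 3.7% |

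The simulated ratios agree with Step 2 (1.63 against 1.61; 1.29 against 1.28). The last two rows are the controls for the argument: with the same selection in both arms, or with access unrelated to outcome, rejection stays near 5%. The error comes from selection that differs by arm combined with a prognostic reason for that selection.

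**The case against.** The strongest reply is about size and scope, and much of it stands.

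- **Size.** Access prevalence, its prognostic effect and the PTA rates are all assumed. At an access cOR of 0.70 with an imperfect marker, the test rejects in about 8 to 13% of trials, so it would usually flag nothing. The larger figures need a stronger prognostic effect or a perfect marker.
- **Different reasons in each arm.** A reader might take this as stated fact. The protocol gives the access reason for controls only. It does not say why or how often PTA is done in the stenting arm, so a different use there is an inference from the absence of any such condition.
- **Onset to groin puncture.** A reader might extend the point to "Onset to groin puncture time (tertiles", which is also usually completed after randomisation. The protocol does not support this. Groin puncture precedes any PTA or stent, no arm-specific rule governs it, and for patients randomised after the first angiographic run it comes before allocation.
- **Consequence.** A reader might fear for the main conclusion. Section 10 rests that on per-protocol and intention-to-treat non-inferiority for the primary endpoint, which this item does not touch. Nor does the protocol say that the subgroup result would guide the choice of patients to stent.
- **Left to the SAP.** Interpretive caveats for subgroups often belong there. But choosing a post-randomisation variable for a predefined interaction test is fixed in the protocol itself.

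None of this makes the PTA strata randomised comparisons.

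**Conclusion.** The point holds in a narrow form and is minor. PTA during EVT is a post-randomisation act by an unblinded operator, under an access condition stated for controls alone, and it should not be the basis of a predefined treatment interaction test.

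The bias needs two things that the protocol neither states nor rules out: selection for PTA that differs between arms, and a relation between difficult access and outcome. The ranges above show what those assumptions would produce and are not a forecast. The primary analysis and the other listed subgroups are outside this conclusion.

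**What to change.** In section 10.4, do one of the following:

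- delete PTA from the list of interaction variables; or
- move it to a separate sentence saying that PTA use and outcome will be reported descriptively, without an interaction test, and labelled as non-randomised.

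The baseline lesion-grade subgroup already in the list stays as it is. It should not be presented as a substitute for access difficulty, because the protocol does not support that use. The onset-to-groin-puncture subgroup needs no change on this account.

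The cost is a wording change, with no new data, no extra patients and no effect on the sample size. It is most credible if made before outcome data by arm are seen.

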#### **10.5 Other study parameters**

The cost-effectiveness will be calculated by comparing the costs for patients with good functional outcome, costs per QALY and costs for the intervention and hospital admissions. Quality of life will be assessed with the EuroQol-5D-5L. Costs for potential productivity loss will be assessed with a set of questions from the iMTA Productivity Cost Care (iPCQ) and costs for any other relevant healthcare resource use will be measured by a set of questions from the iMTA Medical Consumption Questionnaire (iMCQ).

#### **10.6 Interim analysis (if applicable)**

See 9.5

## 11. ETHICAL CONSIDERATIONS

### 11.1 Regulation statement

The study will be conducted according to the principles of the Declaration of Helsinki (October 2013)(33) and in accordance with the Medical Research Involving Human Subjects Act (WMO).

### 11.2 Recruitment and consent

This trial will include patients using a deferred written informed consent procedure. This means that, after the treatment, written informed consent is obtained by asking the patient, or a legal representative of the patient. The justification for the deferred consent is as follows. Firstly, during acute ischemic stroke, the adagium “time is brain” holds. Reperfusion therapy should be initiated as soon as possible. For every hour delay, the chance of recovery to activities of daily living (ADL) independency decreases with 6%. It has been observed in previous acute stroke trials, that obtaining informed consent before start of the treatment, led to an (unacceptable) delay in treatment onset. Secondly, during the acute phase of acute ischemic stroke a patient is often unable to make a well thought out decision on whether to participate in a study, due to neurological deficits like language disturbances, unable to communicate or anosognosia (unaware of his or her medical condition). Obtaining consent from the patient’s proxy will also unacceptably delay the EVT itself. In summary due to the emergency situation as well as the lack of decision-making capacity, the trial cannot be performed without a deferred consent approach. This approach has been successfully used in recent acute stroke trials in the Netherlands.

After treatment, informed consent will be obtained by asking the patient or a legal representative of the patient, preferably within 24 hours after EVT. The patient and/or representative will be provided with a verbal and written explanation of the study by the local investigator. They will be asked for consent to use their data, biomaterials for the purpose of the study and to perform follow up investigations. Participation in the study is voluntary and at any given time, informed consent can be withdrawn. If the patient has died before informed consent has been obtained, the patient’s proxy’s will be informed about the study, the treatment the patient has received and the use of the data that has been collected. Because mortality is an important safety endpoint, data of these patients will be (anonymously) stored, in order to provide these data to the DSMB.

### 11.3 Objection by minors or incapacitated subjects (if applicable)

Minors (patients of 18 years old and less) will not be included in the trial. About 99% of the patients eligible for the trial have acquired neurological deficits due to the stroke interfering with their decision-making capacity. We will follow the procedure as described in 11.2. In the situation that a legally incompetent patient shows behavior suggesting objection to participate in the trial, the patient will not be included in the study. The investigators will adhere to the following code of conduct: ‘Verzet bij wilsonbekwame (psycho) geriatrische patiënten in het kader van de Wet Medisch-Wetenschappelijk Onderzoek met Mensen’ (<http://wetten.overheid.nl/BWBR0009408/2017-03-01>)

#### **11.4 Benefits and risks assessment, group relatedness**

Immediate stenting may be of benefit to the patient, because no second invasive treatment is needed anymore. Moreover, when the carotid artery stenosis has been treated during EVT, the risk of recurrent ischemic stroke is also reduced. Moreover, cohort studies and a systematic review have suggested a better clinical outcome after immediate stenting.

Potential risks of immediate stenting, are the risks of ICH and cerebral hyperperfusion syndrome, although this latter has not been reported in retrospective cohort studies. There is also the need for a longer period of dual antiplatelet therapy (3 months, instead of 3 weeks) in case of immediate stenting, that may increase the risk of hemorrhagic complications.

#### **11.5 Compensation for injury**

The sponsor/investigator has a liability insurance which is in accordance with article 7 of the WMO.

The sponsor (also) has an insurance which is in accordance with the legal requirements in the Netherlands (Article 7 WMO). This insurance provides cover for damage to research subjects through injury or death caused by the study.

The insurance applies to the damage that becomes apparent during the study or within 4 years after the end of the study.

For Belgian participating sites, Art 29 of the Belgian Law relating to experiments on human persons dated May 7th, 2004 applies.

Prior to the start of the Trial, the Sponsor shall enter into an insurance contract in order to adequately cover Trial participants from Belgian sites in accordance with art. 29 of the said law, or delegate this responsibility to the national coordinator.

#### **11.6 Incentives (if applicable)**

The patients will not receive any incentives.

## **12. ADMINISTRATIVE ASPECTS, MONITORING AND PUBLICATION**

### **12.1 Handling and storage of data and documents**

Study data will be entered into a web-based database by the local site investigators. The local investigators will keep a list of research numbers, codes and names. Documents with identifying data will be stored separately from the study and is only accessible to the study coordinator. Pseudonymized imaging data should be sent as DICOM files to the imaging core lab or to the sponsor.

### **12.2 Monitoring and Quality Assurance**

Monitoring schedules will be planned as proposed in the NFU position paper “Kwaliteitsborging mensgebonden onderzoek 2.0. This study will be classified as a moderate risk study, as the risk of SAE’s, like symptomatic intracranial hemorrhage rate, was in previous cohort studies, similar between the immediate CAS and deferred treatment group, and the risk was around 5-10%. The frequency of monitoring will be twice a year in each participating center, performed by an independent study monitor. For the participating centers in Belgium, University Hospital Leuven will arrange the study monitoring (including the French speaking centers), in the Netherlands, the Erasmus MC will arrange the monitoring. The first 3 included patients in each center will be verified for the in- and exclusion criteria as well as informed consent and source data verification of the following variables: age, sex, time of onset, time of groin puncture, NIHSS at baseline, performance of baseline, follow up imaging, SAE’s, study log and documentation. Thereafter source data verification will be performed for 25% of the included patients for the same variables.

### **12.3 Amendments**

Amendments are changes made to the research after a favourable opinion by the accredited METC has been given. All amendments will be notified to the METC that gave a favourable opinion.

Non-substantial amendments will not be notified to the accredited METC and the competent authority, but will be recorded and filed by the sponsor.

### **12.4 Annual progress report**

The sponsor/investigator will submit a summary of the progress of the trial to the accredited METC once a year. Information will be provided on the date of inclusion of the first subject, numbers of subjects included and numbers of subjects that have completed the trial, serious adverse events/ serious adverse reactions, other problems, and amendments.

### **12.5 Temporary halt and (prematurely) end of study report**

The investigator/sponsor will notify the accredited METC of the end of the study within a period of 8 weeks. The end of the study is defined as the last patient’s last visit.

The sponsor will notify the METC immediately of a temporary halt of the study, including the reason of such an action.

In case the study is ended prematurely, the sponsor will notify the accredited METC within 15 days, including the reasons for the premature termination.

Within one year after the end of the study, the investigator/sponsor will submit a final study report with the results of the study, including any publications/abstracts of the study, to the accredited METC.

#### **12.6 Public disclosure and publication policy**

The study database will be closed within one month after the last patient's last visit. A manuscript will be submitted to a major clinical journal within 6 months from closure of the database. The manuscript will be shared with the financial sponsor(s) one month prior to submission, but the financial sponsor(s) will have no influence on its contents.

## 13. STRUCTURED RISK ANALYSIS

### 13.1 Potential issues of concern

#### a. Level of knowledge about mechanism of action

In the intervention group, the carotid artery stenosis is stented during the EVT. The carotid artery stent is placed deployed in the atherosclerotic lesion in the carotid artery by catheterization through the groin. Once the atherosclerotic lesion is being trapped between the stent and the vessel wall, the risk of thrombo-embolism from this lesion is immediately reduced. In the control group, the atherosclerotic lesion in the cervical carotid artery is not stented during EVT, but treated by carotid endarterectomy, CAS or medical management alone, according to the guidelines and dependent on the clinical condition of the patient. In the deferred treatment group, there remains a risk of recurrent stroke until the deferred treatment has been performed, usually within 1-2 weeks after stroke. CAS is a proven and effective technique to reduce the risk of recurrent ischemic stroke in patients with minor stroke or TIA. These RCT's compared CAS with CEA, performed within 1-3 weeks after stroke/TIA. No trials have been performed, assessing the efficacy of CAS in the hyperacute phase during EVT. Observational cohort studies have shown that CAS during EVT is feasible, but results regarding functional outcome and safety endpoints were heterogenous. Most previous studies revealed a better functional outcome in the immediate CAS group at 90 days and no increased risk of intracranial hemorrhage, while some did find a slight increased risk of hemorrhagic complications, associated with the use of dual antiplatelet therapy.

